13. ADVERSE EVENTS

13.1. Definitions and Classifications

Adverse Event (AE) – An AE is “any untoward medical occurrence, unintended disease or injury, or untoward clinical signs (including abnormal laboratory findings) in subjects, users or other persons, whether or not related to the investigational medical device and whether anticipated or unanticipated”.

Note: This definition includes events related to the investigational medical device or the comparator, and to the procedures involved. For users or other persons, this definition is restricted to events related to investigational medical devices.¹

An AE includes any condition (including a pre-existing condition) that:

1. Was not present prior to the study, but appeared or reappeared following initiation of the study.
2. Was present prior to the study but worsened during the study. This would include any condition resulting from concomitant illnesses, reactions to concomitant medications, or progression of disease states.
3. Pregnancy must be documented as an adverse event and must be reported to the clinical monitor and to the Sponsor immediately upon learning of the event.

Clinical Study Protocol

Johnson & Johnson Vision Care, Inc.

Serious Adverse Event (SAE) – An SAE is any adverse event that led to any of the following:

- Death.
- Serious deterioration in the health of the subject that resulted in any of the following:
 - Life-threatening illness or injury.
 - Permanent or persistent impairment of a body structure or a body function.
 - Hospitalization or prolongation of patient hospitalization.
 - Medical or surgical intervention to prevent life-threatening illness or injury or permanent impairment to a body structure or a body function.
 - Chronic disease.
 - Foetal distress, foetal death, or a congenital physical or mental impairment of birth defect.

Diagnoses and conditions that are considered Ocular Serious Adverse Events include, but not limited to:

- Microbial Keratitis (MK)
- Iritis (including cells in the anterior chamber)
- Permanent decrease in best spectacle corrected visual acuity equivalent to 2 acuity lines or greater
- Central Corneal Opacity
- Central Corneal Neovascularization
- Uveitis
- Endophthalmitis
- Hypopyon
- Hyphemia
- Penetration of Bowman’s Membrane
- Persistent Epithelial Defect
- Limbal cell Damage leading to Conjunctivalization

Significant Adverse Events – are defined as events that are symptomatic and warrant discontinuation (temporary or permanent) of the contact lens wear

Diagnoses and conditions that are considered Ocular Significant Adverse Events include, but not limited to the following:

- Contact Lens Induced Peripheral Ulcer (CLPU)
- Significant Infiltrative Events (SIE)
- Superior Epithelial Arcuate Lesions (SEALs)
- Any Temporary Loss of > 2 Lines of BSCVA
- Other grade 3 or higher corneal findings, such as abrasions or edema
- Non-contact lens related corneal events - e.g., Epidemic Keratoconjunctivitis (EKC)
- Asymptomatic Corneal Scar
- Any corneal event which necessitates temporary lens discontinuation > 2 weeks

Clinical Study Protocol

Johnson & Johnson Vision Care, Inc.

Non-Significant Adverse Events – are defined as those events that are usually asymptomatic and usually do not warrant discontinuation of contact lens wear but may cause a reduction in wear time. However, the Investigator may choose to prescribe treatment as a precautionary measure.

Diagnoses and conditions that are considered Ocular Non-Significant Adverse Events include, but not limited to the following:

- Non-significant Infiltrative Event (NSIE)
- Contact Lens Papillary Conjunctivitis (CLPC)
- Superficial Punctate Keratitis (SPK)
- Conjunctivitis: Bacterial, Viral, Allergic
- Blepharitis
- Meibomianitis
- Contact Dermatitis
- Localized Allergic Reactions
- Any corneal event not explicitly defined as serious or significant adverse event, which necessitates temporary lens discontinuation < 2 weeks

Adverse Device Effect (ADE) – An ADE is an “adverse event related to the use of an investigational medical device.

NOTE 1: This definition includes adverse events resulting from insufficient or inadequate instructions for use, deployment, implantation, installation, or operation, or any malfunction of the investigational medical device.

NOTE 2 : This definition includes any event resulting from use error or from intentional misuse of the investigational medical device.”

Unanticipated Adverse Device Effect (UADE) – Any serious adverse effect on health or safety or any life-threatening problem or death caused by, or associated with, the test article, if that effect, problem, or death was not previously identified in nature, severity, or degree of incidence in the investigational plan, Investigator’s Brochure or protocol, or any other unanticipated serious problem associated with the test article that relates to the rights, safety and welfare of subjects.

13.2. Assessing Adverse Events

In conjunction with the medical monitor, the Investigator will evaluate adverse events to ensure the events are categorized correctly. Elements of categorization will include:

- Seriousness/Classifications (see definition in Section 13.1).
- Causality or Relatedness – i.e. the relationship between the test article, study treatment or study procedures and the adverse event (not related; unlikely related; possibly related; related - see definition in Section 13.2.1).
- Adverse Event Severity – Adverse event severity is used to assess the degree of intensity of the adverse event (mild; moderate; severe for all events - see definition in Section 13.2.2).

Clinical Study Protocol

Johnson & Johnson Vision Care, Inc.

- Outcome – not recovered or not resolved; recovering or resolving; recovered or resolved with sequelae; recovered or resolved; death related to adverse event; unknown.
- Actions Taken – none; temporarily discontinued; permanently discontinued; other.

13.2.1. Causality Assessment

Causality Assessment – A determination of the relationship between an adverse event and the test article. The test article relationship for each adverse event should be determined by the investigator using these explanations:

- Not Related - An adverse event that is not related to the use of the test article, study treatment, or study procedures.
- Unlikely Related – An adverse event for which an alternative explanation is more likely, e.g., concomitant treatment, concomitant disease(s), or the relationship of time suggests that a causal relationship is not likely.
- Possibly Related – An adverse event that might be due to the use of the test article, or to the study treatment or study procedures. An alternative explanation, e.g., concomitant treatment, concomitant disease(s), is inconclusive. The relationship in time is reasonable. Therefore, the causal relationship cannot be excluded.
- Related – An adverse event that is listed as a possible adverse effect (device) or adverse reaction (drug) and cannot be reasonably explained by an alternative explanation, e.g., concomitant treatment or concomitant disease(s). The relationship in time is very suggestive, e.g., it is confirmed by de-challenge and re-challenge.

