1.4. Summary of Known Risks and Benefits to Human Subjects

This study will use approved marketed products. The following risks/adverse events can be associated with the use of any marketed contact lens:

- Discomfort, pain, watering or unusual secretions of the eyes
- Redness of the eyes
- Reduced vision and sensitivity to light
- In very rare instances corneal infection, scarring or permanent loss of vision may occur

The key invasive procedures in this work and their associated risks are outlined below:

Staining of the ocular surface with sodium fluorescein

- Some temporary discomfort on application
- Very rarely, anaphylaxis with topical application

There is no direct benefit to the subjects enrolled other than being able to try lens types that they have not had the opportunity to try before. The information obtained from this study may aid in the development of improved contact lenses in the future.

In order to minimize the likelihood of adverse events, subjects will undergo an ocular examination before and after the clinical investigations. Subjects will also be trained on what to do if they develop ocular discomfort, redness, or reduced vision and what to do if they need to be seen outside of the Eurolens Research clinic opening hours.

For the most comprehensive risk and benefit information regarding Acuvue[®] Oasys MAX 1-Day, and Dailies Total 1 refer to the latest version of the package insert of the marketed products (Appendix C).

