11. STUDY TERMINATION

The occurrence of one or more Unanticipated Serious Adverse Device Effect (USADE), or any SAE where the relationship to study agent cannot be ruled out, may result in stopping further dispensing of test article. In the event of a USADE or SAE, the Sponsor may unmask the treatment regimen for the subject(s) and will discuss this with the Investigator before any further subjects are enrolled.

Clinical Study Protocol

Johnson & Johnson Vision Care, Inc.

The Sponsor will determine when a study will be stopped. The Principal Investigator always has the discretion to initiate stopping the study based on patient safety or if information indicates the study's results are compromised.

JJVC reserves the right to terminate the study at any time for any reason. Additionally, the IEC/IRB reserves the right to terminate the study if an unreasonable risk is determined. The study can be terminated by the Principal Investigator at the individual clinical site due to specific clinical observations, if in their opinion, after a discussion with JJVC, it is determined that it would be unwise to continue at the clinical site.

JJVC (and the IEC/IRB and DMC, if applicable) will evaluate all adverse events. If it is determined that an adverse event presents an unreasonable risk, the investigation, or that part of the investigation presenting the risk, will be terminated as soon as possible.

Should the study be terminated (either prematurely or as scheduled), the Investigator will notify the IEC/IRB and Regulatory Authority as required by local regulatory requirements.

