13.3. Documentation and Follow-Up of Adverse Events

The recording and documenting of adverse events (ocular and non-ocular) begin when the subjects are exposed to the test article, study treatment, or study procedure. Adverse events reported before the use of test article, start of study treatment, or study procedures will be recorded as medical history. However, if the condition deteriorates at any time during the study it will be recorded and reported as an AE. Untoward medical events reported after the subject's exit from the study will be recorded as adverse events at the discretion of the Investigator.

Clinical Study Protocol

Johnson & Johnson Vision Care, Inc.

Upon finding an adverse event, the Principal Investigator will document the condition in the subject record and in the eCRFs. He/she will complete the Adverse Event eCRF.

Complete descriptions of all adverse events must be available in the subject record. All Adverse Events including local and systemic reactions not meeting the criteria for “serious adverse events” shall be captured on the appropriate case report form or electronic data system. All adverse events occurring while the subject is enrolled in the study must be documented appropriately regardless of relationship.

It is the Investigator’s responsibility to maintain documentation of each reported adverse event. All adverse events will be followed in accordance with applicable licensing requirements. Such documentation will include the following:

- Adverse event (diagnosis not symptom).
- Drawings or photographs (where appropriate) that detail the finding (e.g., size, location, and depth, etc.).
- Date the clinical site was notified.
- Date and time of onset.
- Date and time of resolution.
- Adverse event classification, severity, and relationship to test articles, as applicable.
- Treatment regimen instituted, including concomitant medications prescribed, in accordance with applicable licensing requirements.
- Any referral to another health care provider if needed.
- Outcome, ocular damage (if any).
- Likely etiology.
- Best corrected visual acuity at the discovery of the event and upon conclusion of the event.

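### Section 13.2.1 labels a combined lens-and-procedure causality scale as test-article causality, so an event caused only by a study procedure cannot be graded Not Related and may be misread as lens-related

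*Combined protocol and SAP*

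**What the plan says.** Section 13.2.1 introduces the causality assessment as "A determination of the relationship between an adverse event and the test article". It then instructs: "The test article relationship for each adverse event should be determined by the investigator using these explanations". Two of the four grades go beyond the test article:

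- *Not Related*: "An adverse event that is not related to the use of the test article, study treatment, or study procedures".
- *Possibly Related*: "An adverse event that might be due to the use of the test article, or to the study treatment or study procedures".

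*Unlikely Related* rests on another explanation being more likely and does not mention procedures. *Related* requires a listed device effect or drug reaction and does not mention procedures either.

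Section 13.1 defines an adverse device effect as an "adverse event related to the use of an investigational medical device". Under Section 13.3, recording of events is to "begin when the subjects are exposed to the test article, study treatment, or study procedure". Section 1.4 sets out the risks of fluorescein separately from those of the lenses, including "Very rarely, anaphylaxis with topical application". Section 11 says that "any SAE where the relationship to study agent cannot be ruled out, may result in stopping further dispensing of test article".

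**The concern.** The label and the content of the scale disagree. The investigator is asked about the lens, but must consider both lens and procedures before choosing *Not Related*. A reaction with a purely procedural cause therefore gets a grade that, under its own label, leaves some relation to the lens open.

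The situation is foreseeable. Both eyes receive fluorescein at the slit lamp examination (Appendix F), and the left eye is held open for up to 30 seconds three times at each visit (steps 1.13, 2.10 and 3.10). What is at stake is the accuracy of the recorded device relationship. A later reader who wants to know which events were adverse device effects would look to this grade, and it does not answer that question cleanly. Section 13.2.1 also speaks of a single test article, although each subject wears two lens types in sequence.

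**Working it through.** The plan states no figure on this point, so the check is a reading of the text in three steps.

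**Step 1. Trace one event through the four grades.** Take an event caused only by fluorescein or by the eye-opening test.

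| Grade in 13.2.1 | Does a procedure-only event fit? |
|---|---|
| Not Related | No. The wording also requires no relation to procedures. |
| Unlikely Related | Usable, if the procedure is taken as the more likely explanation. |
| Possibly Related | Yes, literally, because procedures are named as a possible cause. |
| Related | Poorly. It needs a listed device effect or drug reaction. |

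The grade that would be correct for the lens is the one that is barred. Two investigators could properly choose *Unlikely* and *Possibly* for the same event.

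**Step 2. Check whether the event can arise without a lens.** At Visit 1 the baseline slit lamp examination is step 1.10, the baseline eye-opening test is step 1.13, and the first study lens goes on at step 1.16. Recording of events starts with exposure to a study procedure (13.3). A reaction at 1.10 or 1.13 would thus be graded on a test-article scale before any study lens had been worn. At Visit 2 the first lens comes off at 2.11, the slit lamp examination that allows for fluorescein follows at 2.12, and the second lens goes on at 2.13. Nothing in 13.2.1 says which lens a grade would refer to.

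**Step 3. Compare what other sections need from the grade.**

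| Combined meaning (lens, treatment or procedure) | Lens-only meaning |
|---|---|
| 13.2, definition of causality | 13.1, adverse device effect |
| 13.3, follow-up of ongoing related events | 13.3, list of items to document |
| 13.4, report to the ethics committee | 13.4.1, case-history statement for serious or significant events |

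A procedure-only event has to be related for the left column and not related for the right. One grade cannot give both answers, and the documentation list in 13.3 has no item for relationship to a procedure.

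**Scale.** The documents give no event rate, so an expected number of affected events cannot be calculated. One affected subject would be 1/10 = 10% of the completion target, or 1/16 = 6.25% of maximum enrolment.

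**The case against.** The best case for the plan is that the combined scope is deliberate. Sections 13.2, 13.3 (follow-up) and 13.4 all use it, so only the lead-in to 13.2.1 is loose and correcting one sentence would do. This stands in part. Rewording the lead-in would bring 13.2.1 into line with 13.2, but the lens-only uses would then have no graded answer behind them.

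A reader might also infer several stronger consequences, which the documents do not support:

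- *That a procedure reaction is charged to a lens.* *Unlikely Related* stays open, and nothing says that this grade counts as device-related. A reaction before step 1.16 has no study lens to be charged to, and a subject who leaves at that point is outside the Safety Population (14.3).
- *That causes cannot be separated afterwards.* Section 13.3 requires likely etiology, date and time of onset, and a full description for every event. With at most 16 subjects, each event can be read individually.
- *That a serious procedural event must read as a lens signal.* Section 13.4.1 requires a lens-only statement for serious and significant events. Section 11 refers to the study agent, not to a 13.2.1 grade, and does not say whether that term covers procedures.
- *That related-event rates for each lens are distorted.* None is planned. The by-lens summaries in 14.7 cover other observations, which Section 2.2 lists as slit lamp findings, tear film stability and patient-reported outcomes. Section 14.1 promises safety summaries only in general terms. Counts of instillations or eye openings, and intervals around a hypothetical single event, would not measure this defect.

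These points narrow the consequences. They do not make *Not Related* available for a procedure-only event.

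**Conclusion.** The concern holds in a limited form. As written, the rule gives a wrong code for the lens relationship whenever an event is due only to a study procedure, and such an event may be misread as lens-related.

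The practical effect falls mainly on non-significant events, where the lens-only statement of 13.4.1 is not required. Section 13.1 places localized allergic reactions and superficial punctate keratitis in that class, so a mild procedural reaction could well fall there. Likely etiology and onset time partly mitigate the problem, but nothing says that they override the causality grade. The primary analysis of lens fit is unaffected.

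This rests on reading 13.2.1 literally and on the public documents. The adverse event eCRF is not among them, so a separate procedure field may already exist. If it does, the wording of 13.2.1 would still need correcting.

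**What to change.** In Section 13.2.1, and on the adverse event eCRF if it has no such field already, replace the single grade with two items on the same four grades, with *Not Related* defined for each:

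- (a) Relationship to the test article, identifying the lens or wear period, with procedures removed from the category wording.
- (b) Relationship to study procedures, naming the procedure.

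Use (a) for adverse device effects and for the record of relationship to test articles in 13.3. Use (a) or (b) wherever the text has the combined meaning, as in 13.2, the follow-up rule in 13.3 and the ethics committee report in 13.4. The study-agent wording in Section 11 must be reconciled with these items so that it is clear which relationship is meant.

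The cost is a change of wording and one extra field, with slightly more data entry per event. It adds no visits, tests or subjects.

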13.2.2. Severity Assessment

Severity Assessment – A qualitative assessment of the degree of intensity of an adverse event as determined by the Investigator or reported to him/her by the subject. The assessment of severity is made irrespective of test article, study treatment, or study procedure relationship, or seriousness of the event and should be evaluated according to the following scale:

- Mild – Event is noticeable to the subject, but is easily tolerated and does not interfere with the subject's daily activities.
- Moderate – Event is bothersome, possibly requiring additional therapy, and may interfere with the subject's daily activities.
- Severe – Event is intolerable, necessitates additional therapy or alteration of therapy, and interferes with the subject's daily activities.

13.3. Documentation and Follow-Up of Adverse Events

The recording and documenting of adverse events (ocular and non-ocular) begin when the subjects are exposed to the test article, study treatment, or study procedure. Adverse events reported before the use of test article, start of study treatment, or study procedures will be recorded as medical history. However, if the condition deteriorates at any time during the study it will be recorded and reported as an AE. Untoward medical events reported after the subject's exit from the study will be recorded as adverse events at the discretion of the Investigator.

Clinical Study Protocol

Johnson & Johnson Vision Care, Inc.

Upon finding an adverse event, the Principal Investigator will document the condition in the subject record and in the eCRFs. He/she will complete the Adverse Event eCRF.

Complete descriptions of all adverse events must be available in the subject record. All Adverse Events including local and systemic reactions not meeting the criteria for “serious adverse events” shall be captured on the appropriate case report form or electronic data system. All adverse events occurring while the subject is enrolled in the study must be documented appropriately regardless of relationship.

It is the Investigator’s responsibility to maintain documentation of each reported adverse event. All adverse events will be followed in accordance with applicable licensing requirements. Such documentation will include the following:

- Adverse event (diagnosis not symptom).
- Drawings or photographs (where appropriate) that detail the finding (e.g., size, location, and depth, etc.).
- Date the clinical site was notified.
- Date and time of onset.
- Date and time of resolution.
- Adverse event classification, severity, and relationship to test articles, as applicable.
- Treatment regimen instituted, including concomitant medications prescribed, in accordance with applicable licensing requirements.
- Any referral to another health care provider if needed.
- Outcome, ocular damage (if any).
- Likely etiology.
- Best corrected visual acuity at the discovery of the event and upon conclusion of the event.

In addition, if an infiltrate(s) is present, he/she will complete the Corneal Infiltrate Assessment eCRF. Where necessary, a culture of the corneal lesion will be collected to determine if the infection is microbial in nature. If cultures are collected, the date of culture collection and laboratory utilized will be recorded.

Changes in the severity of an AE shall be documented to allow an assessment of the duration of the event at each level of intensity to be performed. Adverse events characterized as intermittent require documentation of the onset and duration of each episode. Changes in the assessment of relationship to the Test Article shall also be clearly documented.

Subjects who present with an adverse event shall be followed by the Investigator, within licensure, until all signs and symptoms have returned to pre-treatment status, stabilized, or been satisfactorily resolved. If further treatment beyond licensure is required, the patient will be referred to the appropriate health care provider. The Investigator will use his/her clinical judgment as to whether a subject reporting with an adverse event will continue in the study. If a subject is discontinued from the study, it will be the responsibility of the Investigator to record the reason for discontinuation. The Investigator will also document the adverse event appropriately and complete the Adverse Event eCRF. Any subjects with ongoing adverse

Clinical Study Protocol

Johnson & Johnson Vision Care, Inc.

events related to the test article, study treatment, or study procedures as of the final study visit date, should be followed to resolution of the adverse event or until referral to an appropriate health care provider, as recommended by the Investigator. Non-ocular adverse events that are not related to the test article, study treatment, or study procedures may be recorded as “ongoing” without further follow-up.

